6.3 Selection and Timing of Dose for Each Subject

All subjects, whether treated during or in the absence of an acute attack of HAE, will be administered a single SC injection of icatibant.

Subjects treated for an acute attack of HAE should receive icatibant within 12 hours after the onset of the attack. There are no prespecified attack severity criteria that are required for treatment. Subjects with attacks considered to be mild, moderate, or severe are all potentially eligible to receive treatment with icatibant.

Subsequent treatment with icatibant for up to 2 additional attacks of acute HAE, for a total of 3 icatibant administrations, will be offered to pubertal/postpubertal subjects contingent upon having received initial icatibant treatment and presenting with a subsequent acute attack at least 3 days after prior treatment (see Section 4.1.3). For subsequent attacks, study drug may be administered by study site personnel at the hospital/study center or by qualified home healthcare personnel at the subject's home. Alternatively, a parent/legal guardian/caregiver will be allowed to administer or the subject (under the supervision of a parent/legal guardian/caregiver) will be allowed to self-administer the investigational product after having received appropriate training.

For all subsequent laryngeal attacks, subjects should be advised to seek medical attention in an appropriate healthcare facility immediately following treatment with icatibant.

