- Study drug may be administered by study site personnel at the hospital/study center or by qualified home healthcare personnel at the subject's home. Alternatively, a parent/legal guardian/caregiver will be allowed to administer or the subject (under the supervision of a parent/legal guardian/caregiver) will be allowed to self-administer the investigational product after having received appropriate training.
- For all subsequent laryngeal attacks, subjects should be advised to seek medical attention in an appropriate healthcare facility immediately following treatment with icatibant.

The subject will be observed by the investigator, the home healthcare provider or the parent/guardian/caregiver for a minimum of 2 hours after icatibant administration.

The following will occur after icatibant administration:

	Subject Treated at Study Site	Subject Treated at Home
Icatibant Administration	X	X
Investigator Symptom Score	X	
Home Healthcare Provide or Parent/Legal Guardian/Caregiver Symptom Score	X	X
Subject Self-Assessment of Pain	X	X
Injection site reaction evaluation	X	X
Concomitant Medications	X	X
Adverse Events	X	X
Contact site 6 to 8 hours after attack	X	X

- HAE symptoms will be assessed at Day 1, 1 hour [± 10 minutes] post dose and 2 hours [± 10 minutes] post dose AND every 2 hours [± 10 minutes] until the subject's symptoms are absent or mild [if the subject's symptoms are not absent or mild at 2 hours post dose]
 - The investigator will assess HAE symptoms using the Investigator Symptom Score and record the time of initial symptom relief if the subject is treated at the hospital/study center
 - The home healthcare provider will assess HAE symptoms using the Home Healthcare Provider or Parent/Legal Guardian/Caregiver Symptom Score and record the time of initial symptom relief if the subject is treated at home
 - The parent/legal guardian/caregiver will assess HAE symptoms using the Home Healthcare Provider or Parent/Legal Guardian/Caregiver Symptom Score if the subject is treated at either the hospital/study site or at home
- The subject will self-assess pain using diary FPS-R (1 hour [± 10 minutes] post dose and 2 hours [± 10 minutes] post dose, and every 2 hours [± 10 minutes] until pain is absent [if the subject's pain is not absent at 2 hours post dose]);

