10.7 Efficacy Analyses

Efficacy analyses will be performed on the Efficacy Population. The primary efficacy endpoint is the time to onset of symptom relief measured using the investigator-reported symptom score. For the initial icatibant-treated attack, the investigator will report symptom scores at pretreatment and 1, 2, 4, and 6 hours post treatment, and at 8 hours post treatment for subjects who had not shown complete resolution of HAE symptoms at 6 hours. For subsequent icatibant-treated attacks, the investigator will report symptom scores at pretreatment and 1 and 2 hours post treatment, and every 2 hours afterwards until discharge. Eight symptoms will be assessed for abdominal and cutaneous attacks, and 13 symptoms will be assessed for laryngeal attacks. Time to onset of symptom relief is defined as the earliest time post treatment at which there is a 20% improvement in the average post-treatment symptom score with no worsening of any single component score. The median time and the 95% confidence interval will be calculated using the Kaplan-Meier methodology.

A tabular summary of the average investigator-reported symptom score and the change from baseline in the average investigator-reported symptom score will be presented by the stratification group and the icatibant exposure number. An alternative analysis will focus on the time to minimal symptoms and is defined as the time from study drug administration to the earliest time post treatment when all symptoms are either absent or mild. The median time and 95% confidence interval will be calculated using Kaplan-Meier methodology.

For individual investigator-reported symptom scores, a shift table from baseline will be presented for each post-treatment time point. The analysis will be repeated to assess shift in the individual symptom scores from the 2 hour time-point. Also, for individual symptoms that are moderate or worse at pretreatment, the median and 95% confidence interval will be presented for the time to the symptom being mild or absent.

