^a All evaluations and sample collections must be performed at the hospital/study center within 6 months prior to treatment if a repeat attack does not occur within 6 months. If a second “baseline” visit is conducted due to lack of repeat attacks, one of the monthly phone calls may overlap with the onsite visit. In this case, a monthly call would not be necessary.

^b These assessments may be conducted by telephone contact.

^c If a subsequent attack occurs within 3 days of the Day 8 follow-up visit for the previous attack, the visits for Day 1 (of the subsequent icatibant-treated attack) and Day 8 (of the prior icatibant-treated attack) will be combined. If a subsequent attack occurs within 7 days of the Day 90 follow-up visit for the previous attack, the visits for Day 8 (of the subsequent icatibant-treated attack) and Day 90 (of the prior icatibant-treated attack) will be combined.

^d For subjects who have expressed an interest in self-administering or having a parent/legal guardian/caregiver administer icatibant in the home.

^e For subsequent attacks, study drug may be administered by study site personnel at the hospital/study center or by qualified home healthcare personnel at the subject’s home. Alternatively, a parent/legal guardian/caregiver will be allowed to administer or the subject (under the supervision of a parent/legal guardian/caregiver) will be allowed to self-administer the investigational product after having received appropriate training. For all subsequent laryngeal attacks, subjects should be advised to seek medical attention in an appropriate healthcare facility immediately following treatment with icatibant.

^f If after the completion of the assessments scheduled for 2 hours post-treatment, the subject’s pain is absent, no further Day 1 assessments are required. If the subject’s pain at 2 hours post-treatment is NOT absent, the subject will be assessed every 2 hours until pain is absent.

^g For subjects treated at the hospital/study center only.

^h The subject will be observed for a minimum of 2 hours after icatibant administration. If after the completion of the assessments scheduled for 2 hours post-treatment, the subject’s symptoms are absent or mild, no further Day 1 assessments are required. If the subject’s symptoms at 2 hours post-treatment are moderate, severe, or very severe, the subject will be assessed every 2 hours until the subject’s symptoms are absent or mild.

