#### 7.8.1 Investigator Symptom Score

The primary efficacy endpoint is the time to onset of symptom relief measured using the investigator-reported symptom score. Eight symptoms will be assessed for abdominal and cutaneous attacks, and 13 symptoms will be assessed for laryngeal attacks. Time to onset of symptom relief is defined as the duration of time in hours from study drug administration to the earliest time post-treatment at which there is at least a 20% improvement in the composite (or average) post-treatment symptom score with no worsening of any single component score.

Subjects not achieving the onset of symptom relief will be censored at the time of their last symptom assessment. Time to onset of symptom relief will be summarized using the Kaplan-Meier method.

An alternative efficacy endpoint is the time to minimum symptoms measured using the investigator-reported symptom score. It is defined as the earliest time post-treatment when all symptoms are either mild or absent. Subjects not achieving the minimum symptom criteria will be censored at the time of their last symptom assessment. Time to minimum symptoms will be summarized using the Kaplan-Meier method. Subjects with all symptoms as mild or absent at pretreatment will be excluded from this analysis.

The composite investigator-reported symptom score and the change from pre-treatment in the composite investigator-reported symptom score will be summarized by study time-point. Furthermore, the symptom scores associated with individual symptoms will be summarized by study time-point. The mean composite investigator-assessed symptom score will be plotted by study time-point by pubertal status stratification group.

For individual investigator-reported symptom scores, a shift table from baseline will be presented for each post-treatment time point. The analysis will be repeated to assess shift in the individual symptom scores from the 2 hour time-point.

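### In site-treated repeat attacks, scoring may end at 2 h on a criterion other than relief, so some unrelieved attacks are censored there because of their score

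*Protocol*

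**What the plan says.** **Stopping rule.** Protocol 8.4.2.1 scores symptoms in repeat attacks at 1 h and 2 h, and then every 2 h "until the subject's symptoms are absent or mild". Appendix 3 footnote h, repeated in SAP Appendix III (10.3.3), states the consequence: if at 2 h the "symptoms are absent or mild, no further Day 1 assessments are required". Protocol 10.7 differs. It has the investigator score at 1 h and 2 h "and every 2 hours afterwards until discharge". The subject need be observed only "for a minimum of 2 hours after icatibant administration", and repeat attacks have no symptom-based discharge rule like the one for the initial attack.

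**Endpoint.** SAP 7.8.1 names time to onset of symptom relief on the investigator score as the primary efficacy endpoint. It requires at least a 20% improvement in the composite with no component worse. "Subjects not achieving the onset of symptom relief will be censored at the time of their last symptom assessment". Subjects whose symptoms are all mild or absent before treatment are excluded from time to minimum symptoms, but not from time to relief. The analysis covers the initial and both subsequent exposures.

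**Who can be affected.** Protocol 6.3 sets no severity threshold: "Subjects with attacks considered to be mild, moderate, or severe are all potentially eligible to receive treatment with icatibant". Appendix 3 footnote g limits investigator scoring in repeat attacks to subjects treated at the site.

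**The concern.** The stopping rule looks at an absolute state (no item above mild), whereas the endpoint looks at change from pretreatment. An attack can satisfy the first without the second. Where that happens and scoring stops, the attack leaves the risk set at about 2 h because of its own score.

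Kaplan-Meier treats attacks censored at 2 h as having the same later relief rate as those still followed, and those still followed are mainly the ones moderate or worse at 2 h. At stake is the exposure 2 and 3 relief curve beyond 2 h in a small repeat-treatment group (Protocol 4.1.2 asks for at least 10 subjects). SAP 9.7 plans no sensitivity analysis.

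The same schedule handles pain differently. Footnote f continues FPS-R ratings every 2 h until pain is absent. For a subject with any pain at baseline, reaching zero guarantees the one-level improvement that defines FPS-R relief. The symptom-score rule has no such guarantee.

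**Working it through.** The documents give no sample size calculation or target figure for this endpoint, so there is no stated number to reproduce.

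**Step 1: apply both rules to example scores.** Improvement = (pretreatment sum − 2 h sum) / pretreatment sum. The stop is allowed if the highest item at 2 h is 1 or less.

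| Pretreatment to 2 h | Improvement | Component worse? | Relief? | Stop allowed? |
|---|---|---|---|---|
| Two mild items, unchanged | (2−2)/2 = 0% | No | No | Yes |
| Six mild items, one resolves | (6−5)/6 = 16.7% | No | No | Yes |
| One moderate and five mild become six mild | (7−6)/7 = 14.3% | No | No | Yes |
| Five mild, two resolve, one new mild item | (5−4)/5 = 20% | Yes | No | Yes |
| Swelling 2 to 1, nausea 0 to 1 | (2−2)/2 = 0% | Yes | No | Yes |

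All five would be censored at about 2 h if scoring stopped. In an initial attack (Protocol 8.3.2 and 10.7) the same subjects would be scored at 4 h and 6 h, and at 8 h if not resolved by 6 h.

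**Step 2: how often this could happen (assumed range).** Let m be the share of attacks all mild at dosing, taken as 10% to 50%. Take exponential relief times with a median from 1.0 h (initial attacks in this study, Protocol 1.2.2) to 2.5 h (the slowest icatibant median in the controlled adult studies, same section). Suppose every unrelieved mild attack is still mild at 2 h. The share censored at 2 h is m × 0.5^(2/median).

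- Low end: 0.10 × 0.250 = 2.5%. Chance of at least one in 10 attacks: 1 − 0.975^10 = 22%.
- High end: 0.50 × 0.574 = 28.7%. Chance of at least one in 10 attacks: 1 − 0.713^10 = 97%.

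**Step 3: effect on the curve (assumed rates).** Suppose true cumulative relief by 1, 2 and 4 h is 50, 70 and 90% in attacks moderate or worse at dosing, and 40, 50 and 65% in mild ones. Suppose also that all unrelieved mild attacks stop at 2 h and all other unrelieved attacks continue. Among those continuing, the relief probability from 2 h to 4 h is (0.90 − 0.70)/0.30 = 2/3, so Kaplan-Meier relief at 4 h is 1 − (unrelieved at 2 h)/3.

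| Mild share | Relieved by 1 h | Relieved by 2 h | Of those unrelieved at 2 h, censored | Kaplan-Meier at 4 h | True at 4 h | Difference |
|---|---|---|---|---|---|---|
| 20% | 48% | 66% | 0.10/0.34 = 29% | 1 − 0.34/3 = 88.7% | 85% | 4 points |
| 40% | 46% | 62% | 0.20/0.38 = 53% | 1 − 0.38/3 = 87.3% | 80% | 7 points |
| 60% | 44% | 58% | 0.30/0.42 = 71% | 1 − 0.42/3 = 86.0% | 75% | 11 points |

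SAP 7.1 tabulates quartiles, not relief at 4 h. In every row the 25th percentile is 1 h, the median 2 h and the 75th percentile 4 h, with or without the censoring; in the last row the true curve sits exactly on 75% at 4 h. If mild attacks also had a 2/3 chance of relief between 2 h and 4 h, the difference at 4 h would be zero.

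**Step 4: can a quartile move at all?** Take ten invented attacks relieved at 1 h (3), 2 h (1), 4 h (2), 6 h (2) and 8 h (2). Fully scored, the median is 4 h and the 75th percentile 6 h.

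- Two slowest censored at 2 h: quartiles unchanged.
- Four slowest censored: the 75th percentile drops to 4 h.
- All six later ones censored: the curve stays at 0.60 unrelieved, and neither the median nor the 75th percentile can be estimated.

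**The case against.** The case for leaving the plan alone has real weight.

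- **Reach.** Repeat-exposure efficacy is one of the other objectives, the analysis is descriptive without hypothesis testing, and only site-treated repeat attacks carry an investigator score. In 10 attacks, 4 to 11 points is 0.4 to 1.1 attacks. This stands and limits the importance.
- **Direction.** The overstatement in Step 3 needs mild attacks to be relieved more slowly after 2 h, which nothing in the documents supports. The assumed 44 to 48% relieved by 1 h is also slower than the reported initial-attack median of 1.0 h (95% CI 1.0 to 1.1), which enlarges the group at risk of censoring. This stands.
- **Other information.** The investigator's recorded time of initial symptom relief is analysed for both subsequent exposures (SAP 7.8.4), and FPS-R continues until pain is absent. Later improvement need not go unseen. These are separate endpoints, however, and do not repair the relief curve.
- **Visibility.** SAP 7.1 already calls for the percentage censored, plots and listings of each subject's contribution. That will show the censoring, but not its link to pretreatment severity.

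A reader might infer that such an attack can never record relief. The documents do not say so: footnote h makes further scoring not required, which is not a prohibition, and an attack that was mild at dosing but is moderate or worse at 2 h continues to be scored.

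**Conclusion.** The mismatch is real and follows from the documents' own rules. In site-treated repeat attacks, an unrelieved attack with no item above mild at 2 h may stop being scored and is then censored at about 2 h. Protocol 10.7 contradicts 8.4.2.1 and both schedules on when scoring ends. Because censoring depends on the score, it may be informative for the exposure 2 and 3 Kaplan-Meier curve after 2 h. Relief recorded at 1 h or 2 h is unaffected.

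Its size and direction cannot be determined, because the documents give neither the share of repeat attacks that are mild at dosing nor their later relief rate. The 4 to 11 points at 4 h are an illustration under assumed rates that leave the planned quartiles unchanged. The ten-attack example shows only that other patterns could move them.

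Two stronger conclusions are tempting and not supported. One is that repeat-attack relief will be overstated, which rests on the assumed slower late relief in mild attacks. The other is that a planned comparison with exposure 1 is compromised: the SAP specifies no such comparison, although a reader may make one informally.

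**What to change.** **Scoring rule.** Reconcile Protocol 10.7 with Protocol 8.4.2.1, Appendix 3 footnote h and SAP Appendix III 10.3.3 footnote h, so that symptom scoring in repeat attacks continues every 2 h until the relief criterion is met or all items are 0. This changes wording in four places. It adds a few ratings and may lengthen observation of some mild attacks, since the present minimum is 2 h and raters may not otherwise stay.

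**Data already collected.** Add to SAP Table 14.2.1.2:

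- the proportion relieved by the scheduled 1 h and by the scheduled 2 h assessment, both of which precede any permitted stop;
- the number censored at 2 h, split by pretreatment severity (all items mild versus any item moderate or worse);
- a note that the curve after 2 h rests mainly on attacks still moderate or worse at that time.

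Keep the planned Kaplan-Meier estimates. Truncating the curve at 2 h would discard valid later follow-up, and with 58 to 66% relieved by 2 h, as in Step 3, it would make the planned 75th percentile non-estimable. The cost of this part is SAP wording and a few table rows.

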Appendix 4 Modified Sexual Maturation Scale

Stage	Female Breast Stage	Female Pubic Hair Stage ^a	Male Genital Stage	Male Pubic Hair Stage ^a
1 Preadolescent	Elevation of papilla only.	No pubic hair.	Testes, scrotum, and penis are of about the same size and proportion as in early childhood.	No pubic hair.
2	Breast bud stage; elevation of breast and papilla as a small mound, enlargement of areolar diameter.	Sparse growth of long, slightly pigmented downy hair, straight or only slightly curled, appearing on the pubis. Do not consider hair on the labia.	The scrotum and testes have enlarged and there is a change in the texture of the scrotal skin. There is also some reddening of the scrotal skin.	Sparse growth of long, slightly pigmented downy hair, straight or only slightly curled, appearing chiefly at the base of the penis.
3	Further enlargement of breast and areola, with no separation of their contours.	Considerably darker, coarser, and more curled; spreads sparsely over the conjunction of the pubes.	Growth of the penis has occurred, at first mainly in length but with some increase in breadth. There has been further growth of testes and scrotum.	Considerably darker, coarser, and more curled; spreads sparsely over the junction of the pubes.
4	Projection of areola and papilla to form a secondary mound above the level of the breast.	Hair is adult in type, but the area covered by it is still considerably smaller than in most adults. There is no spread to the medial surface of the thighs.	Penis further enlarged in length and breadth with development of glans. Testes and scrotum further enlarged. Further darkening of the scrotal skin.	Hair is adult in type, but the area covered by it is still considerably smaller than in most adults. There is no spread to the medial surface of the thighs.
5	Mature stage; projection of papilla only, owing to recession of the areola to the general contour of the breast.	Adult in quantity and type, distributed as an inverse triangle. Spread to the medial surface of the thighs, but not up the linea alba or elsewhere above the base of the inverse triangle.	Genitalia adult in size and shape. No further enlargement takes place after stage 5 is reached.	Adult in quantity and type, distributed as an inverse triangle. Spread to the medial surface of the thighs, but not up the linea alba or elsewhere above the base of the inverse triangle.
^a DO NOT use development of pubertal hair as evidence of progression to Tanner stage II because this could reflect increased adrenal gland function (adrenarche) in prepubertal subjects and not hypothalamic/gonadal function. The descriptions used in this table are intended to provide guidance for the investigators and may not align with descriptions of pubic hair and pubertal stage in other sources.				

Appendix 5 Faces Pain Scale-Revised (FPS-R)

Faces Pain Scale – Revised (FPS-R)

From *Pediatric Pain Sourcebook*, www.painsourcebook.ca
Version: 7 Aug 2007 CL von Baeyer

[figure not shown]
In the following instructions, say "hurt" or "pain," whichever seems right for a particular child.

"These faces show how much something can hurt. This face [point to left-most face] shows no pain. The faces show more and more pain [point to each from left to right] up to this one [point to right-most face] – it shows very much pain. Point to the face that shows how much you hurt [right now]."

Score the chosen face 0, 2, 4, 6, 8, or 10, counting left to right, so '0' = 'no pain' and '10' = 'very much pain.' Do not use words like 'happy' and 'sad'. This scale is intended to measure how children feel inside, not how their face looks.

Permission for use. Copyright in the FPS-R is held by the International Association for the Study of Pain (IASP) © 2001. This material may be photocopied for non-commercial clinical and research use. To request permission from IASP to reproduce the FPS-R in a publication, or for any commercial use, please e-mail [contact] For all other information regarding the FPS-R contact [contact] (Pain Medicine Unit, Sydney Children's Hospital, Randwick NSW 2031, Australia).

Sources. Hicks CL, von Baeyer CL, Spafford P, van Koraar I, Goodenough B. The Faces Pain Scale – Revised: Toward a common metric in pediatric pain measurement. *Pain* 2001;93:173-183. Bieri D, Reeve R, Champion GD, Addicoat L, Ziegler J. The Faces Pain Scale for the self-assessment of the severity of pain experienced by children: Development, initial validation and preliminary investigation for ratio scale properties. *Pain* 1990;41:139-150.

